2. **Implementation metrics.** We will measure *acceptability* using our post-treatment Parent Satisfaction Scale²², and a Coaches' Satisfaction Scale (under development) to capture Coaches' perceptions of the adapted model relative to the standard approach. Program *quality metrics* will include evaluation of Coaches' fidelity (based on pre-established video-coding methods). We will examine *participant flow* metrics such as referral sources, ages of children, and number referred, eligible, enrolled, and completed, as well as number of sessions attended/missed/rescheduled.
2. **Sub-group and predictor analyses** will explore child factors (e.g., age, sex, baseline language level) and family factors that are facilitators or barriers to treatment uptake and successful outcomes (e.g., parents' educational attainment, current employment, family structure, parent gender)⁴⁰, using data collected from a Family Profile Form used in our previous work²².
3. **Follow-up (treatment group only).** A 10-minute parent-child interaction video will be collected and coded for toddler responsiveness and parent implementation fidelity using the same procedures as for *time 1* and *time 2*.

2.10 Proposed sample size and justification for assumptions underlying power calculations.

We aim to enroll 120 families into the RCT, across the three participating sites.

This project has two phases, differing only by number of participants and funding source. Specifically, phase 1 (funded by Kids Brain Health Network) involves enrollment of 30 families across the 3 participating sites. For phase 2, funds are being sought through CIHR (to be adjudicated in March 2021). If funded, we will submit an amendment to increase recruitment up to 100. The proposed sample ($n = 100$; ~50 per treatment arm) will yield 80% power to detect a medium effect (at alpha = .05)⁴¹. The assumption of a medium effect comes from our previous RCT which yielded $R^2 = .43$ for the same primary outcome²². We will over-sample by 20% (i.e., recruit to $n = 120$) to allow for attrition (see 2.14). Given that this is an individually randomized group treatment trial (with 1 group-based and 1 individually administered arm) analyses will account for the intra-class correlations associated with group participation, as recommended³⁴. If Phase 2 is not funded, we will use data from Phase 1 as pilot data for further funding applications.

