2.19 Has any pilot study been carried out using this design?

We have made *two substantive adaptations to the standard Social ABCs program*, each with some pilot data. First, we developed a **Group-based** protocol for didactic learning and shortened the duration of 1:1 coaching (6 vs. 12 weeks). We have pilot tested the Group adaptation ($n = 45$ in-person families) with positive reports from families and Coaches (see *Report to Alva Foundation*, attached). Preliminary analyses⁴³ reveal significant gains in toddler responsiveness and parent fidelity comparable to those for the original model (see Fig. 1 and 2). Unique to the Group model is evidence of **reduced parenting stress** (Fig 3), which highlights the enhanced clinical impact of a Group-based intervention that goes beyond increased efficiency²⁸. Parents in the Group model also reported improved toddler language (words understood and spoken³⁸ significantly increased, p 's $< .001$), reduced toddler autism symptoms (APSI³⁷ scores decreased significantly from 20.5 to 17.2; $p = .0005$), and high satisfaction (33.1 out of a possible 35).

The second key adaptation to our original model involved developing a **virtual coaching protocol** for the Group model. Our team made this additional adaptation in April 2020, in response to the Covid-19 pandemic, *and we have already piloted this adapted virtual Group model with an additional 22 families (and 11 in progress)*, demonstrating the feasibility and promise of this novel approach. Preliminary analyses of the **virtual Group-based adaptation** reveal outcomes similar to the *in-person Group model*, with comparable gains in parent fidelity (from 30.8% to 72.2%; $p = .009$) and a trend toward reduced parenting stress (from 31.8 to 25.5) similar in magnitude to the in-person values. Although child-level video data have not yet been coded, parent-reported autism symptoms (on the APSI³⁷) decreased significantly (23.2 to 18.5; $p = .004$), and satisfaction was high (32.5 out of 35). Parent-reported toddler language also increased (p 's = .003, .018, respectively for words understood and spoken). ***On all metrics evaluated to date, changes are commensurate across in-person and virtual delivery methods.***

The **adapted, virtual group delivery model** is a promising, innovative and cost-efficient way to provide intervention to toddlers with probable or confirmed autism at the first signs of concern.

3. Trial Management

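### The medium effect behind n = 100 cannot be obtained from the R-squared of .43 given as its source, so the stated 80% power has no traceable basis

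*Protocol*

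**What the plan says.** Section 2.10 of the protocol plans on 100 completers, about 50 per arm, and says that this sample "will yield 80% power to detect a medium effect" at alpha .05. The next sentence gives the origin of that effect: "The assumption of a medium effect comes from our previous RCT which yielded" R-squared = .43, for the same primary outcome.

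The section gives no number or metric for the effect (d, f or f-squared), no test and no sidedness. It does not say whether .43 belongs to the treatment term or to the whole model, and it mentions no discount from the earlier result. It does say that the analysis will account for intra-class correlation from group participation, but the power statement names no ICC.

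Two other places bear on the point. Section 2.16 plans a Poisson or negative binomial model with covariate control for the primary outcome, and neither model returns d or R-squared directly. Section 2.19 says that the group version "shortened the duration of 1:1 coaching (6 vs. 12 weeks") relative to the standard program. Section 1.3 describes the original program as individual and in-person.

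**The concern.** The effect size drives the sample size, and here the protocol commits itself to where it came from. This is a positive statement of derivation, not a detail left for a later analysis plan, so it can be checked. An R-squared of .43 looks far from medium on any usual scale. A reader therefore cannot tell whether the trial was sized on the earlier result, on a deliberate reduction of it, or on a model-fit statistic read as a treatment effect.

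What is at stake is the standing of the 80% figure. Citing .43 suggests that a previous trial backs the planning effect. If it does not, the 80% rests on a conventional label with no metric, and on an unstated choice of test that moves the answer by about ten percentage points.

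**Working it through.** **Inputs from section 2.10.** 50 per arm; alpha .05; power 80%; effect called medium; R-squared .43.

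**Assumed, because the protocol gives none.** Conventional benchmarks: d = 0.5 medium; f-squared 0.15 medium and 0.35 large.

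**Step 1: reproduce the stated 80% from a medium effect.**

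| Reading of medium, N = 100 | Power |
|---|---|
| d = 0.5, two-sided t test | 69.7% (64 per arm needed for 80%) |
| d = 0.5, one-sided t test | 79.9% |
| f-squared 0.15, 6 predictors tested jointly | 81.4% |
| f-squared 0.15, 7 predictors tested jointly | 78.5% |
| f-squared 0.15, 1 predictor tested | 97.0% |

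So about 80% can be reached, but only under choices that the protocol does not state. The joint tests of 6 or 7 predictors are not tests of the treatment term.

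**Step 2: R-squared .43 read as the treatment term alone.**

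- f-squared = .43 / (1 − .43) = .43 / .57 = 0.754. This is about 5 times the medium benchmark (0.754 / 0.15) and more than twice the large one (0.754 / 0.35 = 2.2).
- As a two-group contrast, d = 2 × √0.754 = 1.74.
- At d = 1.74, about 7 per arm gives 80% power two-sided, and 50 per arm gives more than 99.9%.
- In reverse, d = 0.5 corresponds to R-squared = 0.25 / (0.25 + 4) = .059.

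Medium does not come from .43 on this reading.

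**Step 3: R-squared .43 read as the whole model.** The treatment share depends on what the other terms explain, which the protocol does not give. With an assumed covariate R-squared of c, treatment f-squared = (.43 − c) / .57.

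| Assumed c | Treatment f-squared |
|---|---|
| 0 | 0.75 |
| .20 | 0.40 |
| .30 | 0.23 |
| .35 | 0.14 |
| .38 | 0.09 |
| .40 | 0.05 |

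Medium is one possible value, near c = .35, but .43 does not single it out.

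**Step 4: what 50 per arm can detect.** For a two-sided t test at 80% power without clustering, d = 0.566, or about 0.57.

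**Step 5: clustering, for illustration.** Section 2.2 puts 4 to 8 parents in each group. With an assumed ICC of .01 to .10, applied to both arms, the design effect 1 + (m − 1) × ICC runs from 1 + 3 × .01 = 1.03 to 1 + 7 × .10 = 1.70. The detectable difference then runs from about 0.566 × √1.03 = 0.57 to 0.566 × √1.70 = 0.74. Two-sided power at d = 0.5 runs from 68.4% down to 47.0%. Section 2.10 calls one arm individually administered. If only one arm is clustered, the loss is smaller.

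**The case against.** The strongest defence is that planning on medium after seeing something much larger is prudent. If .43 is the treatment term, 50 per arm has ample power for it, and a shorter program, virtual delivery and an active control are sensible reasons to plan for less. This stands as a statement about direction: on that reading the mismatch is harmless to power. It does not rescue the sentence, because section 2.10 says that the medium effect comes from the earlier trial and mentions no reduction. On the whole-model reading, prudence cannot be claimed at all.

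Second, a whole-model R-squared is not empty. It caps the treatment share, and a medium effect is compatible with it. That is correct, so it would go too far to say that the source contradicts the assumption. The fair statement is that the source does not identify it.

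Third, adjustment for baseline raises power. With an assumed baseline correlation of .5, two-sided power at d = 0.5 is 81.5% before clustering. The protocol could have relied on this, but it states no such correlation.

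A reader might also infer from the pilot fidelity, "from 30.8% to 72.2" per cent, against more than 80% in the earlier trial, that the new version must work less well. The documents do not support that. Section 2.19 also reports group-pilot gains similar to those of the original model and similar changes in person and online, although the virtual child videos had not yet been coded.

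**Conclusion.** The point holds as a failed derivation. R-squared = .43 does not yield a medium effect: read as the treatment term it is f-squared 0.75 (d = 1.74), and read as a whole-model value it leaves the treatment effect anywhere from about 0.75 to 0.05 in f-squared over the covariate shares tried. The 80% figure therefore has no support from its cited source. On the plainest reading, d = 0.5 with a two-sided unadjusted comparison, power is 69.7% before clustering.

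Two stronger conclusions are tempting and not supported. One is that the earlier trial showed a large treatment effect, some 3.5 times the planned one (1.74 / 0.5). That needs .43 to be the treatment term alone, which the protocol does not say. The other is that the sample is too small. The mismatch does not show this, since on the treatment-only reading the plan would be conservative. Nor would a null result become uninterpretable, because its confidence interval can be read however the planning effect was justified.

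The conclusion rests on the conventional benchmarks and on d = 0.5 as the meaning of medium, neither of which the protocol gives. The failure of the derivation on both readings does not depend on the choice of test.

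**What to change.** In section 2.10:

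1. Delete the claim that the medium effect is derived from R-squared = .43.
2. Either state that the planning effect is a chosen value, or give the earlier trial's treatment-specific effect with an explicit, reasoned discount for the changed program and comparator.
3. Name the metric, the test and the sidedness.
4. Restate the power to match: without clustering or covariate adjustment, 50 per arm has 80% power for d of about 0.57 two-sided, and about 70% for d = 0.5. Add the larger detectable difference under a stated ICC range.

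It is not enough to write d = 0.5 into the present sentence. Beside n = 100 and 80% power, that would be untrue for a two-sided unadjusted test, which needs 64 per arm.

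The cost is wording only, with no extra patients. The stated power becomes less favourable.

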2.11 If applicable, will health service research issues be addressed?

This is not primarily a health services proposal. However, exploratory investigation of issues related to feasibility (# of families invited, enrolled, completed) and acceptability (via parents' satisfaction ratings) will inform future implementation work. Our ongoing KBHN-funded work focuses on training and community implementation, including health economics analyses, with ongoing consultative support from [name] (Senior Scientist in the Department of Psychiatry and Child Health Evaluative Sciences program at SickKids' Research Institute in Toronto).

2.12 Planned recruitment rate, organization, time period.

Families will be recruited from our three collaborating sites through clinical and research units and community partners. Recruitment will begin in Year 1 (2nd quarter; Q2) and conclude in Year 3 (end of Q1), allowing sufficient time to code and analyze data for manuscript preparation in Year 3 (see Timeline in Appendix C). Per regional populations and enrollment rates in related work, expected recruitment rates are as follows: (Toronto: 50, Edmonton: 40, Halifax: 30). Recruitment is anticipated to be successful based on the current pilot phase (i.e., the number of interested families currently far exceeds our capacity to enroll them). All three sites have been recruiting high-risk infant siblings of children with autism for longitudinal studies for almost two decades, and are thus well known in our respective communities and have established recruitment pipelines through community partners.

2.13 Are there likely to be any problems with compliance?

We will measure both program compliance and treatment fidelity. **Compliance** rates will be measured by the number of training sessions attended. As in our previous and ongoing work, families will be permitted to miss and reschedule up to 3 individual coaching sessions. Families who miss up to two group didactic sessions will receive session content in a subsequent 1:1 session with their coach. Since the program does not require families to use the strategies for any pre-specified amount of time per day, attendance is our best measure of compliance. However, our established measure of parent implementation **fidelity** provides an index of parents' skill acquisition which serves as a proxy for their amount of practice. In our RCT, 87% of families in the treatment condition achieved our target fidelity rate by the end of the program¹⁹.

2.14 What is the likely rate of loss to follow up?

Retention rates of 85-90% are expected, based on our previous RCT²² and current pilot work. In the initial RCT, >90% of families remained at 6-month follow-up (Treatment: 90.3%; Control: 93.8%). Retention in our pilot evaluation of the virtual Group-based model is currently at 86% (19 of 22 have completed the program). Retention rates are anticipated to be similar to previous rates and may be further supported by the virtual nature of the project (i.e., families do not have to travel to participate). However, due to uncertainties associated with family availability (e.g., in response to Covid-19-related changes in work stoppages or isolation practices), we will over-sample to 120 to ensure we reach our target of 100 completers.

2.15 How many centres will be involved?

Three collaborating sites across Canada: Holland Bloorview (Toronto, ON), IWK Health (Halifax, NS), and Glenrose Rehab (Edmonton, AB).

2.16 What is the proposed type of analyses?

The primary analysis will yield a comparison of rates of toddler vocal responsiveness between the two conditions, controlling for the variables described above. The statistical model for the

Primary Outcome will be either a Poisson or negative binomial regression (if there is overdispersion of the counts), using the number of prompts and/or time as offsets and applying the appropriate correlation structure for observations by participant, and controlling for intraclass correlation due to clustering. Growth curve analysis will be used to calculate the trajectory of change in responsive vocalizations over time for each person based on whatever data are available (if at least 2 measurements), and then estimates (imputes) the missing data if the person followed the same trajectory. Otherwise, a worst-case (no vocal response) scenario can be used.

Secondary Outcomes: We will analyze as per the primary outcome for count variables (e.g., video-coded toddler initiations). We will use repeated measures ANOVA or Generalized Estimating Equations for scores (e.g., word inventory, ASD symptoms, parent efficacy, stress).

Exploratory Analyses: (1) *Predictors* of primary and secondary outcomes will first be assessed univariately for their effect on the outcomes, and significant factors will be subjected to multivariate analysis using the appropriate regression model. We will examine the influence of sex (toddlers), parent gender, and parenting roles by entering these factors as covariates. Given that sample size calculations are not done for all these factors, these analyses are exploratory. (2) *Implementation metrics* (feasibility, acceptability) will be examined descriptively.

[figure not shown]
2.17 Proposed frequency of analyses. Analyses will be conducted at two time points: (1) following the end of Phase 1 ($n = 30$), and (2) at the end of the larger trial ($n = 100$).

2.18 Planned subgroup analyses.

Subgroup analyses, run separately for treatment and control groups, will explore effects of: (1) sex: *Do outcomes differ for boy vs. girl toddlers?*; (2) gender: *Are there differences in parent fidelity and self-efficacy based on self-identified parent gender?*; (3) baseline language functioning: *Do outcomes differ for toddlers who begin the program below (vs. at or above) a 12-month language level (based on parent-reported CDI scores)?*

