2.5 What are the planned inclusion/exclusion criteria?

Inclusion Criteria. Eligibility will be based on elevated scores on the Autism Parent Screen for Infants (APSI³⁷) supported by expert clinician impression of red flags for autism spectrum disorder (ASD), or a confirmed diagnosis of ASD made by a qualified professional (parents will be asked to provide the clinical report). Toddlers will be between ages 12 and 42 months at enrollment, having been born between 36 and 42 weeks’ gestation, with birthweight $>2,500$ g and no neurological, genetic, or severe sensory or motor conditions. Participating families must be residing in Ontario, Nova Scotia, or Alberta at the time of participation.

Requirements for participation include ability to comprehend verbal English instructions. Our Parent Training Manual is written at a grade four language level, but concepts are shared verbally and through images, so literacy is not a requirement. Participation is also dependent on access to high-speed internet and willingness to be video-recorded, for cross-site consistency checks and data acquisition. Parents will be asked to limit other social communication intervention programs (e.g., through Speech-Language Pathology, Occupational Therapy, Applied Behaviour Analysis, or related services) to 1 hour per week. Parents will also complete weekly services log to document involvement in such programs. Finally, parents will be encouraged to try not to miss more than 2 sessions in a row. Missed sessions will be rescheduled if possible. However, all families will be invited to provide end-of-study data even if multiple sessions are missed (number of sessions attended will be used as a covariate in analyses). Families may withdraw at any time.

There are no ***exclusion criteria*** other than failure to meet inclusion criteria.

2.6 Proposed duration of treatment period.

Treatment duration is 6 weeks. Time span between data collection time points will range from 7 to 9 weeks to allow for re-scheduling if necessary.

2.7 Proposed frequency and duration of follow up.

Data will be collected for both groups at: baseline (*Time 0*), 6 weeks later (*Time 1; within 6-8 weeks*), and following the next 6 weeks (*Time 2; within next 6-8 weeks*). Time 2 for the treatment group provides follow-up data to examine maintenance of gains in our primary outcome (toddler vocal responsiveness) and parent fidelity.

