2.9 How will the outcome measures be measured at follow up?

Primary Outcome: Toddler vocal responsiveness. Consistent with our previous work^{21,22}, video coding will be used to measure toddlers' vocal responsiveness (proportion of appropriate child vocal responses following a caregiver prompt, from 10-minute video). All video coding will be conducted by blinded research staff with established reliability, per established protocols. *The primary outcome is change in toddler vocal responsiveness from time 0 to time 1.*

***For all parent-child interaction videos**, parents are instructed to: “*play with your child as you typically play*” and reminded that: “*we want to see both of you on the screen as much as possible*”. **Two 10-minute video clips** will be collected and coded per time point (using average per time-point for analyses); **no coaching occurs during data videos**. Videos will be collected by research staff over the virtual platform, saved to virtual drives within institutional firewalls, and shared securely for coding, based on formal data-sharing agreements. **Blinded research staff with established inter-rater reliability will code all videos, per established protocols.**

Secondary Outcomes (all measures used in our previous and/or ongoing work):

1. *Toddlers.* (a) Vocal initiations and (b) social orienting (both blind-coded from video); (c) parent-rated word inventory (MacArthur-Bates Communicative Development Inventory [CDI]³⁸); (d) autism symptoms (APSI³⁷). 2. *Parents.* (a) Correct use of *Social ABCs* strategies (%)

implementation fidelity from blind-coded video), (b) self-efficacy (Parent Self-Efficacy Scale²² developed for our previous work), (c) parenting stress (Parenting Stress Index-4-Short Form³⁹).

Exploratory Analyses:

1. **Predictor variables:** Continuous (parenting stress, child age, baseline word inventory, ASD symptoms) and categorical (toddler sex, parent gender, parenting role, educational attainment, employment, ethnicity, English spoken at home, family structure), variables (collected from the *Family Profile Form*²⁴) will be assessed for their effect on the outcomes;

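### Section 2.16 does not say how Time 0 enters the primary test of change; modelling Time 1 adjusted for Time 0 responsiveness would be more precise than either likely reading

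*Protocol*

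**What the plan says.** Protocol section 2.9 defines the outcome: "The primary outcome is change in toddler vocal responsiveness from time 0 to time 1".

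Section 2.16 describes the analysis: "The primary analysis will yield a comparison of rates of toddler vocal responsiveness between the two conditions, controlling for the variables described above". The model is described as follows: "Primary Outcome will be either a Poisson or negative binomial regression (if there is overdispersion of the counts), using the number of prompts and/or time" serving as offsets. The same sentence continues with "applying the appropriate correlation structure for observations by participant, and controlling for intraclass correlation due to clustering". The next sentence adds that "Growth curve analysis will be used to calculate the trajectory of change in responsive vocalizations over time for each person", and goes on to use those trajectories to fill in missing data.

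The variables that could be the ones described above come from earlier sections. Section 2.9 lists predictors under its exploratory analyses. The continuous ones open with "Continuous (parenting stress, child age, baseline word inventory, ASD symptoms", and demographic factors follow. Section 2.5 says that the "number of sessions attended will be used as a covariate in analyses". Neither place lists the child's own vocal responsiveness at Time 0.

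Section 2.7 collects data in both arms at Time 0, Time 1 and Time 2. Section 2.2 has the baseline video recorded before allocation is revealed, and lets control families receive the programme once their control period ends.

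**The concern.** The outcome is a change, but the test is worded as a comparison of rates. Nothing in section 2.16 connects the two. It does not say whether Time 0 is a repeated outcome, a covariate or absent, and it does not say which coefficient decides the trial. The reference to variables described above does not close the gap. The baseline word inventory is a parent-rated measure and not the video-coded outcome, and sessions attended is known only after randomisation.

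Precision in the deciding test is at stake. A child's own earlier value of the outcome is the natural covariate, and this design already collects it. The choice should also be made early, because section 2.17 plans an analysis after Phase 1 (n = 30), and an unnamed contrast could then be chosen with results in view.

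**Working it through.** **Inputs.** From section 2.10: about 50 per arm, alpha .05, a medium effect, 80% power claimed. The protocol gives neither a numerical effect size nor sidedness, so I assume 0.5 SD and a two-sided test. It gives no Time 0 to Time 1 correlation r, so I use 0.3 to 0.7. SDs are taken as equal at both visits and clustering is ignored.

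**The plan's own figure.** Normal approximation: power = Φ(δ / (σ√(2/n)) − 1.96). With δ = 0.5, σ = 1 and n = 50, √(2/50) = 0.2, so 0.5/0.2 = 2.5 and Φ(2.5 − 1.96) = Φ(0.54) = 70.5% (69.7% from the noncentral t). The stated 80% is not reproduced by this unadjusted test. It is reached under assumptions that section 2.10 does not state: a one-sided .05 test (80.4%), a multiple-regression F test with f² = 0.15 and 6 predictors (N = 98), or baseline adjustment with r about 0.46 (80.4%).

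**The three ways of testing.** Randomisation makes the expected arm difference zero at Time 0, so all three target the same 0.5 SD difference. Only the SD changes.

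| Analysis | SD σ | r = 0.3 | r = 0.5 | r = 0.7 |
|---|---|---|---|---|
| Time 1, unadjusted | 1 | 70.5% | 70.5% | 70.5% |
| Change, or arm-by-time with free baseline means | √(2(1−r)) | 56.1% | 70.5% | 89.8% |
| Time 1 adjusted for Time 0 | √(1−r²) | 74.6% | 82.3% | 93.8% |

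Example at r = 0.3. Change: σ = √1.4 = 1.183, 2.5/1.183 = 2.113, Φ(0.153) = 56.1%. Adjusted: σ = √0.91 = 0.954, 2.5/0.954 = 2.621, Φ(0.661) = 74.6%.

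**Why adjustment is the most precise.** 1 − r² is below 1 for any r other than 0. Also 1 − r² = (1 − r)(1 + r), which is below 2(1 − r) whenever r is below 1. So for any positive correlation below 1 the adjusted analysis has the smallest variance of the three.

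**In sample size.** For 80% power, n per arm = 2(1.96 + 0.842)²σ²/0.25 = 62.8σ². That is 63 unadjusted, and 58, 48 and 33 adjusted at r = 0.3, 0.5 and 0.7.

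**Check in a count model.** A Poisson simulation was run with 400 trials, 50 per arm, an assumed rate ratio of 1.35 at Time 1 (log 0.300), a base rate of 0.3 per prompt, and about 45 prompts per visit. The SDs on the log scale were 0.5 between children and 0.35 between visits. Power was 58% for Time 1 only, 63% for arm-by-time, and 73% for Time 1 adjusted for Time 0. Mean estimates were 0.301, 0.293 and 0.295, so all three recover the effect and differ in precision.

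**The case against.** The best defence reads sections 2.9 and 2.16 together. The outcome is fixed as change, and section 2.16 asks for "applying the appropriate correlation structure for observations by participant". Because section 2.9 averages the two clips within a time point, several observations per child most naturally means several visits, Time 0 included. The natural test is then arm-by-time, which in a count model compares rate changes between arms and so does express the defined outcome. This stands: it would be wrong to say that change cannot enter the model.

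A reader might infer more: that the condition effect is averaged over Time 0 and Time 1. That would halve the effect to 0.25 SD, with σ = √((1+r)/2) and power of 34% to 27% for r from 0.3 to 0.7. Adding Time 2, with control families caught up, would give 21% to 15%. The documents do not support either inference. The first sets aside the outcome definition in section 2.9. Against the second, section 2.1 separates the parallel-group comparison from the own-control and growth-curve components, section 2.7 gives Time 2 in the treated arm to maintenance, and section 2.9 labels follow-up as treatment group only.

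A reader might also infer that every listed predictor goes into the primary model. Section 2.9 places them under exploratory analyses, and section 2.16 screens them one at a time there.

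Lastly, model terms and covariate lists are often left to an SAP, and one may exist. So the point does not rest on missing detail. It rests on a stated outcome and a stated comparison that are not connected, and on a better analysis of data already planned. The growth-curve sentence does not connect them either: it serves missing data, and section 2.1 describes growth curves for the treatment group.

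**Conclusion.** The point holds in a limited form. Section 2.16 does not say how Time 0 responsiveness enters or which term tests the change. Both likely readings are valid under randomisation, but neither is the most precise. Adjusting Time 1 for Time 0 gives about 75% to 94% power, against 56% to 90% for change or arm-by-time and 70% for Time 1 alone. Over the unadjusted Time 1 test the gain is about 4 points at r = 0.3 and 23 at r = 0.7. Over the change contrast it is about 18 points at r = 0.3 and 4 at r = 0.7.

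These figures rest on an assumed 0.5 SD effect, an assumed correlation, a two-sided test and no clustering. Group clustering would lower all of them. The ordering follows from the variance formulas for any positive correlation below 1. The effect would be diluted only if the condition effect were averaged over Time 0 as well, and the text does not clearly say that.

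**What to change.** In section 2.16, replace the opening sentence on the primary analysis with wording such as: the primary analysis models Time 1 responses, with prompts as denominator, on arm, adjusting for the child's Time 0 responsiveness; the arm coefficient is the primary test. An equivalent choice is one model for Time 0 and Time 1 with a common baseline mean for both arms, testing the arm-by-time term. The common mean matters, because with free baseline means the test falls back to the precision of a change score.

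State that Time 2 is excluded from this test, and keep the listed predictors in the exploratory analyses. Use the Time 0/1/2 labels of section 2.7 throughout, since the Arm A text in section 2.2 numbers the same visits 1, 2 and 3.

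The cost is a short edit here and a matching line in any SAP. No new data are needed: section 2.2 already has the Time 0 video collected before allocation is revealed, and section 2.9 already has video coded at each time point.
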